## **Intervention**

The treatment intervention is a digital transdiagnostic work-focused cognitive behaviour therapy program. The program consists of seven modules (See Table 1 for an overview, and Appendix B for an in-depth review of the modules) consisting of psychoeducational texts, imagery and models, in addition to therapist-tailored tasks for the

participants. The treatment model is based on traditional CBT principles and adjusted to target transdiagnostic maintaining mechanisms in anxiety and depression such as frequent negative emotions and aversive reactions to these that leads to various forms of avoidant coping that serve to reinforce the negative emotional cycle.

*Table 1.*

The modules of the digital program eBehandling – Health and Work

Module 1	Introduction to the program
Module 2	Where can I get help? How can I support myself?
 Module 3	Self-help through constructive and supporting thoughts
Module 4	Helpful actions
Module 5	Working with/through the body
Module 6	Emotions
Module 7	Put it all together and relapse prevention

Treatment will be given by trained eTherapists with specific training in the eBehandling - health and work protocol. They will be given a two-day certified course in work-focused therapy delivered by the National Centre of Competence at Vinderen DPS. Further they will be given a one-day introduction on the use of W-CBT within a digital format by the authors of the program. Further supervision will be facilitated by the research fellow. Adherence and fidelity will be measured through reading eTherapist-participant correspondence and will be rated by the main author of the treatment protocol ([name]) and the main author of the Norwegian translation of W-CBT, [name].

## Statistical analyses

**Quantitative analyses.** In order to identify factors associated with treatment success and outcomes, hierarchical linear mixed modelling analyses (HLM, “multilevel”) will be conducted. In longitudinal HLM, measurement occasions (time) are nested within participants. Fixed effects are average (main) effects, and do not vary across subjects. Random effects vary across subjects and/or measurement occasions (e.g., a random intercept model vs a random intercept, random slope model). In these models, data may be missing at random and at different occasions for different subjects (Tasca & Gallop 2009). The models will be checked if they fulfil the model assumptions of normality of residuals, linearity and homoscedasticity. The dependent variables are sick leave, work related self-efficacy (as measured by RTWSE-11), depression severity (PHQ-9), anxiety (GAD-7), well-being, symptoms, risk and function (CORE-OM) and impairment in functioning (WSAS). The predictors are: Treatment (time), duration of sick-leave prior to treatment, treatment credibility, work related self-efficacy, depression severity and adherence. Comparisons are modelled through main effect and interaction effect analysis (e.g. Time x “Baseline work absenteeism” interaction). Predictors will be centred using grand mean centering. T-values and degrees of freedom will be estimated using “Satterwaite” correction (Luke 2017). The effects sizes will be converted from *t*-values and degrees of freedom to Cohen’s *d* using the R-package “effectsize”. Estimating indirect effects (mediation), we will apply “causal mediation analysis” (CMA), that is a method to split a total effect of an independent predictor (X) into a direct (C) and indirect effect (M). The indirect effect is transmitted through a mediator to the outcome. CMA will be conducted under the assumption of sequential ignorability. The X will be measured at baseline, the M at intermediate treatment, and the outcome(s) at post-treatment (Zhang et al. 2016). See Figure 2 below for a tentative model.

[figure not shown]

Figure 2. Model of mediation.

Corrections for multiple analyses will be done by using Jaccard's correction (Jaccard, 1998) to decrease risk of Type I error when applying several statistical tests.

**Qualitative analyses.** Transcribed interviews will be analysed with the software NVivo 14 using reflexive thematic analysis (Braun & Clarke 2006, Binder, Holgersen & Moltu 2012, Braun & Clarke 2019). By comparing the individual accounts, we want to identify both patterns of commonalities and differences in participants' experiences and formulate these as themes. This phenomenological and interpretive qualitative approach can serve to explore experiences of self in contexts, interpretations of events, narrative structuring and meaning making processes closely, providing important descriptions of patient experiences that may contribute to detect challenges with the treatment protocol and improve the future delivery of the intervention. We have not set a prior hypothesis for the qualitative analysis, as we wish to explore the data inductively and to formulate themes as richly as possible in accordance with

participants' responses. Care will be taken to stay close to the wording and narratives of participants, grounding our findings in their experiences rather than our preconceived notions as researchers.

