## Methods and procedures

### Design

This study is a non-randomized, single arm, multi-center mixed methods clinical trial in a naturalistic setting (see Figure 1 for an overview of the study design). Participants are recruited in a real life setting in Norwegian specialised mental health care. After recruitment participants fill out questionnaires pre, interim and post treatment, in addition to follow up at 6 and 12 months after completing treatment. Interim measures are collected after six weeks. After the treatment intervention, some participants are invited to an in-depth qualitative interview.

[figure not shown]

Figure 1. Study design.

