## Power analyses

In a multilevel model, the fixed effects are comparable to ordinary repeated t-tests, and thus, using this as a proxy model with a moderate effect size ( $d = 0.6$ ), power = 0.8, alpha = 0.05, tails = "two.sided", we need 25 subjects for detecting a single main effect Murayama, Usami and Sakaki (2022); see [Summary-statistics-based power analysis \(shinyapps.io\)](#). But, as stated by Van Voorhis and Morgan (2007): "*if the circumstances allow, a researcher would have better power to detect a small effect size with approximately 30 participants per variable*" (page 48). Following this rule of thumb, we plan for 30 participants per predictor (unique main effects), thus a total sample size of 300 participants. Calculating a drop-out rate of 30% gives a total sample size of  $N = 390$ . Calculating power for indirect effects – or mediation – we used the following online shiny app [Monte Carlo Power Analysis for Indirect Effects \(shinyapps.io\)](#), published by Schoemann, Boulton and Short (2023). Using (El Alaoui et al. 2015) as a proxy study for the direction and strength of association between our variables, they found that both treatment credibility and treatment adherence were significantly predictors of faster change and lower post treatment scores in a routine psychiatric care based ICBT for social anxiety disorder. In the same study, a high level of treatment credibility was associated with higher treatment adherence. Hence, defining X = treatment credibility, M = treatment adherence and Y = treatment outcomes, we set the correlation of X-M (a-path) = 0.3 ( $SD = 1$ ), X-Y (c-path) = 0.30 ( $SD = 1$ ) and M-Y (b-path) = 0.30 ( $SD = 1$ ), power = 0.8, alpha = 0.05, setting random seed to "0512", using 5000 replications with 20000 Monte Carlo draws per replication, we need  $N = 155$  to have a power of 0.80, 95% CI [0.79-0.82].

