## Procedure

Inclusion will be open for 18 months, planned from September 2024. Participants will be recruited from outpatient specialised mental health care facilities in the Western Norway Regional Health Authority and South-Eastern Norway Regional Health Authority. After recruitment, each participant will undergo an assessment for eligibility where inclusion and exclusion criteria are evaluated. If eligible, participants are asked to sign a written informed consent to participation before enrolment in the study. Participants will receive access to the program after consent has been given, using level four secure login, for example BankID or Buypass ID. Participants receive a short tutorial of the program by their eTherapist. When logged in the first time, and as a mandatory task before given access to the program, participants are asked to revise their consent in regards to their unidentifiable data being used in research. Participants can at any time during treatment withdraw their consent. In this case they will be able to continue treatment, but their user data will not be exported for research purposes. Demographic variables and questionnaires will be given as a mandatory task before the first module and are registered directly in the program. The program is set to take 12 weeks to finish.

The main form of contact between participant and eTherapist will be via asynchronous messages. If asked for by the participant, or evaluated as necessary by the eTherapist there will be contact via phone or face-to-face. If a participant fails to log in for more than seven days the eTherapist will make contact via phone or SMS giving them an appointment to evaluate further progress. If a patient drops out of the program the eTherapists are to use their local procedures to how this person is taken care of, see also section for Ethical Considerations.

After 12 weeks the participants will be given a concluding session face-to-face where the next step is decided: End treatment, further treatment within the specialist mental health

care services or referred to a different treatment option. Regardless of this the participants will have access to the treatment program, without therapist contact, for six months after completion.

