### **Monitoring suicidal risk or behaviour**

Participants will each week answer question 10 (suicidal ideations) of the Montgomery and Åsberg Depression Rating Scale (MADRS; Malt, 2016; Montgomery & Asberg 1979) and the total CORE-10. Both of these questionnaires have a cut-off for risk which, if surpassed, leads to an automatic text message and e-mail to the participants' eTherapist and local program supervisor. The eTherapist, or the program supervisor contacts the participant and follows their local procedure on assessing suicidal risk and take precautionary measures as deemed necessary. This will include a face-to-face evaluation and assessment of the level of care needed. The process and conclusion will be documented in the participants electronic journal (EPJ).

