## **Data and privacy protection**

The Youwell platform and concerns of health information have been processed and approved for clinical use via the Western Norway Regional Health Authority based on a risk and vulnerability analysis and Data Protection Impact Assessment (DPIA, See Appendix D for the DPIA). The process in regard to research within a clinical setting is started within Helse Vest and is scheduled to be finished before July 2024. Regarding the specific considerations concerning data extraction this has been evaluated together with a data protection officer (PVO) using a DPIA. Data will be extracted by the PhD candidate using a researcher's access. This grants access to all the reports on self-evaluation and program usage, bar free text answers. It does not give access to the personal profiles of the participants, nor their activities in the program. The export is further limited by default to exclude any who have withdrawn their consent during treatment. Data will be encrypted and saved on secure storage area from Helse Vest IKT and on safe storage (SAFE) at UiB.

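### The weekly CORE-10 has no role in handling drop-out, so the single-arm pre-post symptom change can be biased if leaving depends on current distress

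*Protocol*

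**What the plan says.** Protocol, Statistical analyses (Quantitative analyses), plans longitudinal mixed models and gives their basis for incomplete data: "In these models, data may be missing at random and at different occasions for different subjects". It lists the dependent variables (sick leave, RTWSE-11, PHQ-9, GAD-7, CORE-OM, WSAS) and the predictors (time, prior sick-leave duration, credibility, work-related self-efficacy, depression severity, adherence). The CORE-10 is in neither list, although Measures names it among the secondary outcome measures.

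Design fixes the occasions: "After recruitment participants fill out questionnaires pre, interim and post treatment, in addition to follow up at 6 and 12 months after completing treatment". It adds: "Interim measures are collected after six weeks". Procedure gives the length: "The program is set to take 12 weeks to finish". Power analyses provides for loss: "Calculating a drop-out rate of 30% gives a total sample size" of 390.

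The weekly data appear elsewhere. Under Monitoring suicidal risk or behaviour: "Participants will each week answer question 10 (suicidal ideations", a MADRS item, with the total CORE-10 answered alongside it. Under Data and privacy protection, on the researcher's access: "This grants access to all the reports on self-evaluation and program usage, bar free text answers".

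**The concern.** Missing at random is always conditional on what the model contains. A participant whose questionnaires stop between pre and week 6 has only a baseline score from the treatment period. One whose questionnaires stop between week 6 and post has nothing later than week 6. What happened to that person's distress in the weeks before leaving is held in the weekly CORE-10, which the listed models do not use.

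The Protocol itself describes a route from current distress to leaving. Passing a risk cut-off on the weekly forms leads to a face-to-face evaluation of the level of care needed. The section on drop-out foresees that participant and eTherapist may agree that the programme is unsuitable. Departures of this kind are plausibly missing at random given the weekly scores, and less plausibly so given the listed variables alone.

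The trial has one arm, so no control group with similar drop-out can offset the bias. H2 is about the size of the symptom reduction, which is the quantity affected.

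**Working it through.** **Inputs from the Protocol.** 30% drop-out and N = 390; d = 0.6 called moderate (Power analyses); occasions at pre, week 6, post, 6 and 12 months (Design); 12-week programme (Procedure); weekly CORE-10 (Monitoring suicidal risk or behaviour).

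**Assumed, because the Protocol gives no figure.** The drop-out mechanism, the correlation r of an outcome with the CORE-10, the SD of individual slopes, and 0.8 as the mark for a large effect. Each of the first three is shown over a range.

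**Step 1. The plan's own figures.** A paired t-test at d = 0.6, two-sided 0.05, has power 0.804 at n = 24 and 0.821 at n = 25, so the stated 25 is reproduced to within one. N = 390 is 300 × 1.3. If the 30% means missing post scores, that is 0.3 × 390 = 117 people.

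**Step 2. What a given bias requires.** Bias = share missing × gap, where the gap is how much more improvement the model credits to leavers than they truly had, in baseline SDs.
- From 0.60 to 0.62: gap = 0.02 / 0.3 = 0.07 SD.
- From 0.60 to 0.73: gap = 0.13 / 0.3 = 0.43 SD.
- From 0.60 to 0.80: gap = 0.20 / 0.3 = 0.67 SD. Leavers would truly have changed by 0.80 − 0.67 = 0.13 while credited with 0.80.

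**Step 3. Simulation without covariates.** Weekly CORE-10 has baseline SD 1, a random slope and autocorrelated error, and 30% leave. The weekly log-odds of leaving rise by β per SD of CORE-10; exp(β) is 1.6 at β = 0.5, 2.7 at β = 1 and 7.4 at β = 2. Negative β means that improvers leave. True d is 0.59 to 0.60 in every cell. The table gives the likelihood estimate from pre, week 6 and post:

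| r, slope SD | β = −1 | 0 | 0.5 | 1 | 2 |
|---|---|---|---|---|---|
| 0.8, 0.6 | 0.53 | 0.60 | 0.63 | 0.68 | 0.74 |
| 0.8, 1.0 | 0.48 | 0.60 | 0.66 | 0.71 | 0.81 |
| 0.3, 0.6 | 0.56 | 0.60 | 0.61 | 0.63 | 0.65 |

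With the weekly CORE-10 added, every cell returns 0.59 to 0.60. A second set of runs, with odds multiplied by 1.6 to 4.5, gave 0.62–0.73 for r of 0.6 to 0.8, 0.61–0.65 for r = 0.3, 0.50–0.57 if improvers leave, and about 0.60 throughout with the weekly scores.

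**Step 4. Credit for what the model already contains.** Random-intercept model, true d 0.59, odds × 2.7, half of the leavers assumed to answer follow-up:

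| Information used | Slope SD 0.6 | Slope SD 1.0 |
|---|---|---|
| Time only | 0.68 | 0.76 |
| Plus adherence | 0.62–0.66 | 0.69–0.73 |
| Plus adherence and follow-up scores | 0.61–0.63 | 0.66–0.68 |
| With weekly CORE-10 | 0.59 | 0.59 |

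The listed variables shrink the bias but do not remove it. The remainder is 0.02–0.04 or 0.07–0.09.

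**Step 5. Against the standard error.** At N = 390 the simulated standard error is about 0.067 (0.0675 without the weekly scores, 0.0666 with them). The remainder in step 4 is 0.02/0.067 to 0.04/0.067 = 0.3 to 0.6 standard errors with narrow slopes, and 0.07/0.067 to 0.09/0.067 = 1.0 to 1.3 with wide ones. Using the weekly scores costs no precision.

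**Step 6. On the Protocol's own effect-size scale.** The Protocol converts t and df to d. For the simplest mixed model at N = 390 (true d 0.60, slope SD 0.6, r = 0.8), t/√df is 0.45, 0.52 and 0.58 at β = 0, 1 and 2, and 2t/√df is 0.89, 1.03 and 1.15. The bias moves both, but neither changes side of 0.8.

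**The case against.** **This is analysis-plan detail.** The quoted sentence describes mixed models correctly and excludes no auxiliary variable, and an analysis plan that is not shown may add one. That is fair, and the point is not that the sentence is false. But the section does more than name a model: it commits to lists of outcomes and predictors, and a weekly measure that the Protocol itself counts as a secondary outcome is in neither.

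**The models see more than pre and week 6.** This stands. Adherence, baseline covariates and the 6- and 12-month scores also carry information. Leaving treatment is not the same as giving no further data, since follow-up is requested by SMS, and the Protocol does not say which of the two its 30% means. The step 3 figures are therefore an upper range and step 4 is the fairer guide.

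**The remedy works by construction.** In the simulation leaving depends only on the CORE-10, so adding it must recover the truth. In practice other reasons for leaving will remain, and the weekly scores would reduce the bias rather than abolish it. Participants who withdraw consent during treatment are excluded from export and cannot be helped this way.

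**A reader might infer that a moderate change would be reported as large.** The documents do not support that. H1a and H2 give no threshold and no decision rule. From the Protocol's own 0.6, reaching an assumed 0.8 takes roughly seven-fold weekly odds per SD together with widely varying slopes. From a true 0.70 the estimate is 0.78–0.81 at β = 1 and 0.84–0.91 at β = 2, but only with covariates and follow-up ignored and on the baseline-SD scale. On the t-to-d scale no crossing was shown.

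**The primary outcomes gain little.** Largely right for sick leave if its correlation with the CORE-10 is low; 0.3 is an assumed value. No figure specific to RTWSE-11 is available.

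**Conclusion.** The point holds as a worthwhile improvement to the stated method. Apart from the single suicidality item asked with it, the weekly CORE-10 is the only record of a participant's state just before leaving, and the analysis gives it no role. If leaving depends on current distress, the pre-post change in PHQ-9, GAD-7 and CORE-OM is biased: a true 0.60 becomes about 0.62–0.73 under moderate to strong dependence with adherence and follow-up ignored, and more only in extreme settings. With them used, at the middle strength of dependence, the remaining bias is 0.02–0.09. It does not shrink with sample size.

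The direction is unknown, because improvers leaving would make the estimate too low. All sizes rest on an assumed drop-out mechanism, correlation and slope spread. The conclusion also assumes that the weekly forms count as self-evaluation reports for export, which is the natural reading. No claim is made that a moderate effect turns into a large one.

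**What to change.** In Statistical analyses, state that the H2 time effects, and the CORE-OM change, will be estimated with all weekly CORE-10 scores up to drop-out as auxiliary information. Two routes serve: multiple imputation of post and follow-up scores from all earlier outcomes plus the weekly CORE-10, or a joint mixed model of the outcome and the CORE-10. Report the estimate without the weekly scores alongside, so that the reader sees what they change. The same can be done for sick leave (H1a) and RTWSE-11 (H3) as a sensitivity analysis.

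Confirm that the weekly forms are in the research export, and say whether the 30% refers to leaving treatment or to missing assessments.

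The cost is a little more analysis work. The data are already collected, participants answer nothing extra, and precision is not lost.

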## **Hypotheses of main effects**

**H1a.** We expect a large main effect of treatment on total percentage sick leave from pre- to post treatment, with gains maintained at follow up.

**H1b.** We expect a large main effect of treatment on the number of participants with full return to work from pre- to post treatment, with gains maintained at follow up.

**H2.** We expect a large main effect of treatment on reduction on symptoms of depression and anxiety.

**H3.** We expect a positive main effect of treatment on Return to Work Self-Efficacy, from pre to post treatment, and sustained through follow up.

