## Sample

Inclusion criteria for the sample are 1) being an outpatient in specialised mental health care service, 2) above 18 years old, 3) full or graded sick leave, or on work assessment allowance 4) primary diagnosis of F30 – F40 (ICD-10), 5) currently employed.

Exclusion criteria are 1) ongoing psychotic disorder and/or mania, 2) ongoing substance abuse, incl. sedative medications, 3) ongoing episode of major depression, 4) organic brain disease, 5) severe reading and writing difficulties.

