## Measures

**Demographic variables.** Self-reported data will be collected on gender, age, level of education, length and degree of sick leave, length of mental health problems and marital status. Primary and secondary F-diagnosis (ICD-10) will be reported by the eTherapist.

**Questionnaires.** *Primary outcome measures:* The reduction in the degree of sick leave is one of our primary outcomes and will be measured through self-report. The first question is: “are you currently on sick-leave?”. The second question is activated if there is a positive answer to the first: ” To what degree are you currently on sick-leave?”. The answer is given on a 0-100 scale with 5 point increments.

The Return to Work Self-Efficacy Scale (RTWSE-11; (Lagerveld et al. 2010, Gjengedal et al. 2021) is an 11-item questionnaire measuring an individual’s confidence in their ability to work and perform work tasks. Items are scored on a scale from 1 (“Totally disagree”) to 6 (“Totally agree”). Items 2 and 6 are reversed. Total scores of 3.7 or below are associated with less probability of returning to work, while scores of 4.6 and above are associated with increased probability of returning to work (Gjengedal et al. 2021).

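### The protocol commits 0-100 sick leave to a linear mixed model with normal, equal-variance residuals and no fallback, and gives full return to work (H1b) no model

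*Protocol*

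**What the plan says.** Under Statistical analyses, the protocol plans hierarchical linear mixed models for the quantitative outcomes, with Satterthwaite degrees of freedom and t-values converted to Cohen's d. Sick leave heads the list of dependent variables; the others are questionnaire scores. On assumptions it says: "The models will be checked if they fulfil the model assumptions of normality of residuals, linearity and homoscedasticity". It does not say what happens if they are not fulfilled. Random intercepts and random slopes are both mentioned, and neither is chosen.

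Under Measures, the degree of sick leave is one of the primary outcomes. A yes/no question comes first, and the degree is asked only after a yes. "The answer is given on a 0-100 scale with 5 point increments".

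Under Sample, participants enter on "full or graded sick leave, or on work assessment allowance". Under Hypotheses of main effects, H1a concerns percentage sick leave, and H1b reads: "We expect a large main effect of treatment on the number of participants with full return to work". Full return to work does not appear among the dependent variables, and no logistic or other binary model is named.

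**The concern.** A score that is bounded, recorded in steps and fed by a yes/no question should not be expected to have normal residuals of equal variance. After entry, everyone who answers no to the first question has to be scored 0, so a group at 0 follows from the design, and H1b predicts that the group will be large. The spread will therefore change from wave to wave.

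Three things are at stake.

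- **Intervals.** A single residual variance shared by all waves can give wrong standard errors for the pre-post and later contrasts.
- **An open primary analysis.** The checks are likely to fail for a primary outcome, and the replacement would then be chosen after the data are seen.
- **H1b.** A headline hypothesis about a yes/no outcome has no stated analysis.

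A fourth matter concerns H4. The protocol's own example of an interaction is time by baseline absenteeism. On a bounded scale such a term can move because of the limits of the scale.

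**Working it through.** **1. The plan's own figure.** Power analyses treats the problem as a paired comparison: "the fixed effects are comparable to ordinary repeated t-tests". With d = 0.6, two-sided alpha 0.05 and power 0.80, the normal approximation gives n = (1.960 + 0.842)² / 0.6² = 7.85 / 0.36 = 21.8, so 22. The exact paired t-test gives 24 (power 0.804), with power 0.821 at n = 25. The stated 25 is reproduced within one or two. It concerns a continuous change score, so it says nothing about H1b or about unequal variance. The planned analysed number is 300, which is used below.

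**2. Where the interval error comes from.** Take complete data, categorical time, a random intercept and one residual variance σ². The model's standard error for any wave against entry is √(2σ²/N). The actual one is √(Var(Dj)/N), where Var(Dj) = V1 + Vj − 2·C1j is the variance of the change from entry to wave j. The two agree at every wave only if all these change variances equal 2σ². With variances that differ by wave, the pooled value is too large for some contrasts and too small for others.

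**3. Size for the 0-100 score.** The protocol gives no distribution, so three were assumed. A latent normal score was rounded to 5 and cut at 0 and 100, with N = 300, complete data and 2000 runs per cell. Monte Carlo error is √(0.95 × 0.05 / 2000) = 0.5 percentage points.

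| Assumed crowding | At 100 on entry | At 0 at post | Coverage, post vs entry | Coverage, week 6 vs entry |
|---|---|---|---|---|
| Light | 28% | 11% | 94.6-96.2% | 96.1% |
| Moderate | 48% | 24% | 94.6-94.9% | 97.1% |
| Heavy | 66% | 30% | 93.3-94.4% | 97.5% |

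Intervals built from the paired differences of the same data covered 94-96% throughout.

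A heavier case used 71% at 100 on entry, 38% at 0 at post and n = 390 × 0.7 = 273. It gave 91-92% at post, 6 and 12 months, and 98% at week 6. Its standard error for post against entry was 1.86 points by the model and 2.11 in fact: 1.96 × 1.86 / 2.11 = 1.73, which corresponds to about 92%. A further check gave 94-97% at post and follow-up and 96-99% at week 6, against 94-96% with paired standard errors.

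**4. Size for full return to work, if it went into the same model.** A yes/no outcome has variance p(1 − p). Under heavy crowding the assumed proportions fully returned are 0, 0.05, 0.30, 0.44 and 0.52 over the five waves. The variances are 0, 0.05 × 0.95 = 0.048, 0.30 × 0.70 = 0.21, 0.44 × 0.56 = 0.246 and 0.52 × 0.48 = 0.250. Equal variance fails by construction. Simulated coverage was 96-97% at post and 99.7-100% at week 6, so the intervals are too wide. A plain proportion needs no such assumption: at p = 0.30 and N = 300, the 95% half-width is 1.96 × √(0.21/300) = 0.052.

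**5. The interaction term.** In the same simulations, a baseline predictor was related to sick-leave level but not to latent change. The linear Time x predictor test at post was significant in these shares of runs:

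| Predictor's correlation with level | Light | Moderate | Heavy |
|---|---|---|---|
| 0.3 | 7-8% | 15-16% | 42-44% |
| 0.5 | 11% | 32% | 82% |

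With a predictor unrelated to level it was 3-6% over all three settings, and on the uncut latent score 4-6%. The interval for the interaction on the observed 0-100 scale still covered 94-96%. The term estimates a true difference in mean percentage points, for example about 3.5 points per unit of the simulated predictor under heavy crowding at correlation 0.3.

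**The case against.** **The statistical analysis plan is not shown.** A fallback after an assumption check, and a model for one further outcome, are often placed there. This has force for H1b, where the protocol is silent. It has less force for sick leave, because the protocol already fixes the model family, the dependent variables, the test and the effect size.

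**The interval error is small and rests on assumptions.** This stands. Graded leave and work assessment allowance are also eligible, so crowding at 100 on entry is not established. Only the group at 0 after entry follows from the design. The protocol also leaves random slopes open, and these allow the variance to change over time. The simulations used a random intercept only and no missing data.

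**A reader might infer that the linear model produces false predictor effects.** The documents do not support that. H1a is about percentage sick leave itself, and nobody can be more than fully absent, so a difference in mean percentage points is real on the scale that the protocol chose. It is false only relative to an assumed latent scale, and only for predictors related to level. Among the named hypotheses it bears chiefly on the moderation sentence of H4.

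**A reader might infer that full return to work has been assigned to the linear model.** It has not. It is absent from the list, and the figures in step 4 show only what would follow by default.

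**A cumulative-logit model of post degree, with baseline degree as covariate, might look like the cure for the interaction.** It is not. With the same latent predictor effect before and after, a check gave 24-35% rejection for the linear interaction and 52-54% for the cumulative logit at a latent shift of 0.2. At a shift of 0.4 the figures were 63-82% and 96-98%.

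**Conclusion.** The point holds in a limited form. The protocol puts a bounded primary outcome into a model with normal, equal-variance residuals, plans to check those assumptions and gives no action if they fail. It leaves H1b without a model.

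The numerical consequence for mean change is modest. Intervals are mainly too wide at week 6 (96-99% coverage). The error at post and follow-up is small in most settings (93-97%), with 91-92% in the heaviest one tried. These figures assume a random intercept, complete data and entry distributions that the protocol does not report.

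For H4, a Time x predictor term may partly reflect the ceiling or floor when the predictor is related to entry level. How far it does so cannot be known from the documents. No stated sample size or power figure changes.

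**What to change.** Amend Statistical analyses as follows.

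1. **Sick leave, 0-100.** Keep mean change in percentage sick leave at each wave, with time as categorical. Use an unstructured covariance, or person-level robust or bootstrap standard errors, so that each contrast has its own variance. State this in advance, so that the assumption check no longer decides the primary analysis.
2. **Full return to work.** Add it as a binary dependent variable. Report the proportion with a 95% interval at post, 6 and 12 months. No pre-post test is needed, because the entry proportion is at or near zero by inclusion. This assumes that participants on work assessment allowance are counted as not returned at entry. The two sick-leave questions do not settle that, so the definition should. For predictors, use a logistic model that handles data missing at random, such as a mixed logistic model. An unweighted logistic GEE would generally need a stronger missing-data assumption than the planned mixed models, with 30% drop-out expected.
3. **H4.** State that a Time x predictor term on this scale is a difference in mean percentage points that may partly reflect the ceiling or floor when the predictor is related to entry level. Do not read it as moderation on that basis alone. Do not replace it with the cumulative-logit model discussed above.

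The cost is wording only: no new data and no change to the sample size. Odds ratios read less directly than percentage points, so predicted probabilities of full return should be shown beside them.
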